##### Exclusion criteria:

- Maternity admissions during/after pregnancy
- Patients admitted or undergoing abdominal surgery for a second time or more

### **8. SAMPLE SIZE**

This study will identify patients diagnosed with an intestinal emergency who may require surgery and observe patient outcomes, and how they correlate with the treatment they received. Trial analysis of all admissions in 2018 identified 901 patients with an abdominal emergency, 59% (530) of which had surgical intervention, either a laparotomy or a laparoscopy. Scaling these numbers to the study period of 6.5 years, we expect to identify a total of over 5,800 patients with an intestinal emergency and over 3,400 patients undergoing surgery. All UK hospitals have to submit data on all their intra-abdominal procedures to the National Emergency Laparotomy Audit (NELA). From previous analysis of PHUT NELA data (11), at least 30% of patients having an operation will have been completed laparoscopically. This is a remarkably large proportion of laparoscopic procedures compared to the UK average (8% according to NELA database) and will provide us over 1,000 laparoscopies in our study data set.

The PHUT data set includes a sufficient number of outcomes for model development (rule of thumb: 10 outcomes per predictor variable (25)). This study will be looking at a patient population with high mortality. Initial analysis of 2018 data identified in-hospital mortality as the rarest outcome with 23 deaths (4.3%) of patients having surgery and 28 deaths (7.6%) of patients not having surgery. Other outcomes occur in greater numbers. Collective numbers for the 6.5 year study period will therefore provide us with enough outcomes for the development of logistic regression models. The data set will be tested for separation and Firth's correction applied if necessary (26). Based on these numbers, we will be able to establish statistically significant correlations from this data set from a single hospital.

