Study Participants	
Data will be derived from electronic patient records collected as part of routine clinical patient care on all general adult wards (excluding maternity) between 2013 and 2020.
 
Inclusion criteria:
 
 
• Must have an acute intestinal condition, based on their ICD-10 codes and OPSC-4 codes
 
• Must be <math>\geq 16</math> years of age at the time of admission
 
• Have at least one full set of vital signs recorded on the day of admission
 
• Have at least one full set of routine blood tests recorded on the day of admission
 
 
Exclusion criteria:
 
 
• Maternity admissions during/after pregnancy
 
• Patients admitted or undergoing abdominal surgery for a second time or more
 
 
Using OPCS-4 codes from PAS and TheatreMan™ and NELA data, we will then identify patients who had an emergency laparotomy, and those who had a laparoscopic procedure. We aim to identify a further group where treatment is futile, suggesting that an early focus on end of life care might be appropriate.

Planned Sample Size	2,500
Follow-up duration	1 year (retrospectively)

Planned Study Period	01 Dec 2020 – 31 May 2021
Primary Objective	Provide mortality rates for different treatment options, and analysis of short- and long-term outcomes.
Secondary Objectives	Define patient sub-groups with similar health characteristics based on clinical data and an established risk index.  Use statistical analysis to predict the risk of death for each patient group and treatment option, which will allow us to identify the best care pathways for each cluster.
Primary Endpoint	Mortality risk for each treatment group
Secondary Endpoints	Risk of other outcomes and long-term complications and association between patient factors and these outcomes
Intervention (s)	N/A

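### The synopsis plans 2,500 patients but section 8 expects over 5,800, and section 8's claim of enough outcomes rests on two pooled groups although four group models are planned

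*Protocol*

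**What the plan says.** **Sample size.** The synopsis row "Planned Sample Size" reads 2,500. Section 8 starts from 901 patients in 2018, of whom 530 had surgery, scales to 6.5 years and states: "we expect to identify a total of over 5,800 patients with an intestinal emergency and over 3,400 patients undergoing surgery". It adds that "at least 30% of patients having an operation will have been completed laparoscopically", and that this "will provide us over 1,000 laparoscopies in our study data set". Section 7.4 takes in every qualifying patient and then screens against the eligibility criteria.

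**Outcomes for modelling.** Section 8 relies on a "rule of thumb: 10 outcomes per predictor variable". It calls in-hospital death the rarest outcome, with "23 deaths (4.3%) of patients having surgery and 28 deaths (7.6%) of patients not having surgery" in 2018, and says of the rest: "Other outcomes occur in greater numbers". It concludes: "Collective numbers for the 6.5 year study period will therefore provide us with enough outcomes for the development of logistic regression models".

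**Planned models.** Section 10.2 divides the data into four treatment groups, screens candidate predictors of 30-day mortality, and builds a logistic model with non-linear terms in each group. Section 6.2 names the four pathways: laparotomy, laparoscopy, other alternative treatment and end of life care.

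**The concern.** Two points arise from the Protocol's only sample-size justification.

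First, 2,500 and over 5,800 both stand as the size of the study. The reader cannot tell which one the surgical and laparoscopy counts, and the statement about outcomes, belong to.

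Second, a rule of events per predictor applies to the data set in which a model is fitted. Section 8 counts events in two pools, but the models are fitted in four groups. Objective 3 uses these models to identify the best care pathway for a patient's characteristics, so each model's own event count matters, and a pooled count cannot supply it.

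**Working it through.** **Inputs.** From section 8: 901 patients in 2018, 530 with surgery (so 901 − 530 = 371 without), 6.5 years, a laparoscopic share of at least 30%, and 23 and 28 in-hospital deaths. From the synopsis: 2,500. From section 4.2: a 60% laparoscopic share by 2018.

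**1. Section 8's own figures reproduce.**
- All patients: 901 × 6.5 = 5,856.5 (stated: over 5,800).
- Surgical: 530 × 6.5 = 3,445 (stated: over 3,400).
- Laparoscopic: 0.30 × 3,445 = 1,033.5 (stated: over 1,000).
- Non-surgical: 371 × 6.5 = 2,411.5 (not stated).

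**2. The synopsis figure does not follow from these inputs.**
- 2,500 / 5,856.5 = 0.427, which is 57% fewer patients.
- 2,500 / 901 = 2.8 years of admissions at the 2018 volume, against 6.5.
- 3,445 surgical patients already exceed 2,500.

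**3. What 2,500 would imply at the same case mix.**
- Surgical: 530 × 2,500 / 901 = 1,471.
- Laparoscopic at the 30% share: 0.30 × 1,471 = 441.
- Laparoscopic at the 60% share: 0.60 × 1,471 = 882, still below 1,000.
- In-hospital deaths: 23 × 2,500 / 901 = 64 surgical and 28 × 2,500 / 901 = 78 non-surgical.

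**4. Events behind the sufficiency sentence, at section 8's cohort size.**
- Surgical pool: 23 × 6.5 = 149.5.
- Non-surgical pool: 28 × 6.5 = 182.

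**5. Events against planned models.**

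| Planned model (sections 6.2 and 10.2) | Patients given in section 8 | Deaths given in section 8 |
|---|---|---|
| Laparotomy | not separately | only within the surgical pool |
| Laparoscopy | over 1,000 | only within the surgical pool |
| Other alternative treatment | none | none separately |
| End of life care | none | none separately |

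No row has its own event count. The number of candidate predictors is not fixed either, so the rule of 10 cannot be evaluated for any of the four models. The deaths counted are in-hospital, whereas section 10.2 names 30-day mortality.

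**The case against.** **The study is a census of existing records.** No recruitment target or power calculation depends on 2,500, and the synopsis still carries template text, so the field may simply not have been updated. This limits the practical consequence. It does not remove the contradiction, and the text does not establish that explanation.

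**Screening could reduce 5,800 to 2,500.** Eligibility requires full vital signs and full blood tests on the day of admission (section 7.4). Only the first intervention counts (section 7.4), and the national opt-out applies (section 9.2). Any of these could lower the count, but none is quantified or linked to 2,500. Section 8 also places its laparoscopies in the study data set, so its figures cannot all be counts before screening. A reader might infer from the completeness above 97% in section 10.2 that screening could remove only about 3%. That does not follow: the figure describes nearly complete data within 24 hours, which is a different window and standard from full sets on the day of admission.

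**Section 8's claim is about accumulation over years.** The word collective can fairly be read as adding up the 6.5 years, not as pooling groups for modelling. Even so, the supporting counts are for two groups and the models are for four.

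**Detail by model belongs in an analysis plan.** Event counts and parameter limits can be left to one. An unqualified statement in the Protocol that the outcomes are enough is a different matter, because it is already made on a basis that does not match the models.

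**Safeguards exist.** Firth's correction if separation is found (section 8) and 10-fold cross-validation (section 10.2) are useful, but they do not supply an event count for each group.

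**A stronger reading is tempting:** that some group models have too few events. A reader might split the 150 surgical deaths by the 30% share and read off a number of predictors. The Protocol does not support that. Its deaths are in-hospital, and it says other outcomes are more frequent. The 2018 deaths came from a year when section 4.2 puts the laparoscopic share at 60%. It gives no size for the mortality difference between approaches, and no split of the non-surgical deaths.

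**Conclusion.** Both parts hold, within limits.

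The sample size is stated inconsistently: 2,500 against about 5,856, a difference of about 3,356 patients that nothing in the Protocol explains. The effect on the stated counts is material, with about 441 laparoscopies at 2,500 instead of over 1,000. That figure assumes the 2018 case mix throughout and section 8's 30% share.

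The statement that outcomes are enough is unsupported for the models planned, because it rests on about 150 and 182 in-hospital deaths in two pools while four models are to be fitted. This is a gap in the argument, not a demonstration that events are too few. Thirty-day deaths will be more numerous by section 8's own statement, by an amount it does not give.

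**What to change.** 1. State one expected analysed sample size in both the synopsis and section 8. Show the derivation of any reduction from the day-of-admission data criterion, first-intervention-only counting and the opt-out. Restate the surgical and laparoscopy counts to match.

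2. Replace the sufficiency sentence in section 8 with the expected 30-day deaths in each of the four treatment groups, tabulated from the 2018 extract and scaled to the study period. In any group where deaths outnumber survivors, give the survivors, since the smaller count limits the model. Confine the claim to groups that meet the Protocol's own rule of 10 per parameter, counting non-linear terms as parameters.

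The cost is a wording change and one tabulation of data already extracted. No patients are added and the planned models stay as they are. The downside is that the stated modelling capacity may look less favourable than the pooled figures suggest.

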### **6.2 Objectives**

1. Identify all patients with a condition that would qualify them for emergency abdominal surgery, both laparotomy and keyhole (laparoscopic) procedures, regardless of whether they had surgery

or not. This will be done by filtering electronic hospital records for appropriate diagnosis and operation codes.

2. Provide updated estimates of the average risk of death for different treatment options, including surgical and non-surgical intervention, using statistical analysis of short-term and long-term outcomes. Describe health characteristics of the typical patient population receiving one of the treatment options, based on their clinical data and an established risk index.
3. Logistic regression will be used to predict the risk of death for each patient group and each treatment option, which will allow identification of the best care pathways given a patient's health characteristics.
4. Identify patients who would have likely benefited from a different care pathway than the one they received, using machine learning classification algorithms

Our analysis will form the foundation for the establishment of four well-defined care pathway options, each with the patient's best interest in mind: laparotomy, laparoscopy, other alternative treatment, and end of life care.

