### 10.2 Data analysis

Extracted data will be cleaned and quality controlled prior to analysis to ensure all relevant patients have been extracted. Given that our analysis will use only routinely collected, clinical data, missing values are unlikely to pose an issue. Initial analysis of 2018 data confirmed that clinical data within 24h of admission was almost fully complete for a remarkable >97% of admissions, meaning there is likely no need to impute data. We will test whether excluding admissions with missing data will introduce bias.

Our analysis can be broken down into the following steps:

- Comparison of the four treatment groups based on demographics, outcomes and medical pathway. This will include calculating mortality and long-term complication rates (Objective 2).
- Construct and compare risk models for each treatment group to predict short-term and long-term risk and to investigate the effect of both patient and hospital-level factors on outcome (Objective 3).

- Identify patients in each group who are abnormal for the group and might have fared better with a different treatment, using clustering algorithms (Objective 4).

After splitting the data set into subsets for each of the four patient groups using diagnosis and procedure codes (see above), mortality and long-term complication rates will be calculated for each group. Longer-term follow-up will include rates of re-admission to hospital, additional theatre visits and development of new medical conditions, within one year of initial admission with an abdominal emergency. Results will provide updated estimates of the average risks of different surgical procedures as well as the risk of not having surgery. Results will be compared with P-POSSUM mortality. Patient groups will further be characterised the using patient factors. Parameters of interest will include but are not limited to age, sex, mortality, long-term complication rates, admission early warning scores (NEWS, LDTEWS and LDTEWS:NEWS), frailty, medical history (previous ICD-10 codes).

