Patient group characteristics will be summarised with proportions for nominal and ordinal variables, means and standard deviations for continuous variables having symmetric unimodal distributions, and medians and interquartile ranges for other continuous variables. Clinical outcomes will be reported as proportions with 95% confidence intervals. Statistical tests of differences in proportions (Chi - nominal variables) and means/medians (ANOVA/Kruskal-Wallis) will be performed. Post-hoc pairwise comparisons will be carried out using Scheffe's method for ANOVA and Dunn's test for Kruskal-Wallis results and Bonferroni corrections for Chi results with significance at  $p < 0.05$ .

In the next step, we will identify which patient characteristics affect the outcome for a specific care pathway. Candidate predictor variables of 30-day mortality will be assessed with simple univariable linear regression and check for non-linearity. For each treatment group, we will construct a logistic regression model with the candidate predictor variables and non-linear terms as needed. Logistic regression performance will be tested using "goodness of fit" and discrimination. Goodness of fit, the ability to correctly predict risk, will be evaluated using the Hosmer-Lemeshow statistic (28) and by 10-fold cross-validation. Discrimination, the ability to rank cases in terms of risk, will be assessed using the Area Under the Receiver Operating Characteristic Curve (AUROC) (29). The relative importance of individual parameters will be assessed by the parameters Wald and t-statistics.

The last objective is to determine outlier clusters of patients who might have fared better on a different care pathway. For each treatment group, machine learning classification algorithms will be used to identify homogenous clusters of admissions in terms of their attributes. Each clustering will be reported by its method, number of clusters and intracluster correlation coefficients (ICCs) with 95% confidence intervals and used to extend the logistic regression risk model for the treatment group to see if the model is improved as measured by a likelihood ratio test. Where this is the case the patient subgroups corresponding to the clusters will be analysed in terms of their clinical characteristics.

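### If separation triggers plain Firth correction, mean predicted risk of death shifts towards one half, so the predicted risks need an intercept correction

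*Protocol*

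**What the plan says.** Protocol Section 8 (Sample size) names the remedy and its trigger: "The data set will be tested for separation and Firth's correction applied if necessary (26". Use is conditional on separation being found, and no other remedy is named.

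The models are for prediction. Section 6.2, objective 3, says: "Logistic regression will be used to predict the risk of death for each patient group and each treatment option", and the best care pathway is to be identified from the result. Section 10.2 plans to "Construct and compare risk models for each treatment group to predict short-term and long-term risk" and then works with 30-day mortality: "Candidate predictor variables of 30-day mortality will be assessed with simple univariable linear regression". One logistic model is to be built per treatment group, and there are four groups.

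For the amount of data, Section 8 reports that the 2018 trial analysis "identified 901 patients with an abdominal emergency, 59% (530) of which had surgical intervention", with "23 deaths (4.3%) of patients having surgery and 28 deaths (7.6%) of patients not having surgery" (in-hospital deaths). It also gives a rule of thumb of ten outcomes per predictor. Calibration is to be checked by the Hosmer-Lemeshow statistic and 10-fold cross-validation (Section 10.2). No action is attached to a poor result, and the protocol does not mention re-estimating the intercept or otherwise recalibrating Firth predictions.

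**The concern.** An ordinary maximum-likelihood logistic fit has an intercept equation that forces the predicted risks, summed over the patients in the fit, to equal the number of deaths. Firth's penalty changes that equation. It keeps coefficients finite under separation and reduces their bias, but the summed predictions no longer match the deaths, and the difference is in the direction of a risk of one half. For odds ratios this hardly matters. For absolute risks it is a calibration error in the average prediction.

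Predicted risks are to be compared between treatment options. If separation occurs in a small group and not in a large one, the first would be predicted with a shifted average and the second without. Part of an apparent difference between pathways could then come from the estimator.

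**Working it through.** **The plan's own figures, reproduced (Section 8).**
- Patients: 901 × 6.5 = 5,856.5. With surgery: 530 × 6.5 = 3,445. Both agree with "we expect to identify a total of over 5,800 patients with an intestinal emergency and over 3,400 patients undergoing surgery".
- Laparoscopy: the protocol expects that "at least 30% of patients having an operation will have been completed laparoscopically", so 0.30 × 3,445 = 1,033.5, agreeing with its figure of over 1,000. Laparotomy: 3,445 − 1,033.5 = 2,411.5.
- No surgery: (901 − 530) × 6.5 = 371 × 6.5 = 2,411.5.
- Mortality: 23/530 = 4.34%; 28/371 = 7.55% (printed as 7.6%; the difference is immaterial here).
- Deaths over 6.5 years: surgery 23 × 6.5 = 149.5; no surgery 28 × 6.5 = 182. Laparoscopy 0.30 × 149.5 = 44.85 and laparotomy 0.70 × 149.5 = 104.65, assuming that both share the 4.3% rate.

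**Mechanism.** Firth's score equation for the intercept gives

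sum of predicted risks = deaths + Σ hᵢ(½ − pᵢ),

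where pᵢ is the fitted risk and hᵢ the leverage of patient i. The hᵢ sum to the number of parameters, k + 1 for k predictors. The added term is positive when the leverage-weighted mean risk is below one half, as in all the low-mortality settings below, and negative when it is above. It can never exceed (k + 1)/2 deaths, so with D deaths the relative excess is at most (k + 1)/(2D), whatever the covariate effects.

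**Size.** The protocol gives no predictor count, so k is assumed. The simulated ratios (150 to 300 data sets per setting) also rest on assumed covariate effects and a few rare binary predictors.

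| Group | D | k | D/k | Ceiling (k+1)/(2D) | Simulated mean predicted / observed |
|---|---|---|---|---|---|
| Laparoscopy | 44.85 | 4 | 11.2 | 2.5/44.85 = 5.6% | 1.045 |
| Laparoscopy | 44.85 | 10 | 4.5 | 5.5/44.85 = 12.3% | 1.09-1.10 |
| Laparoscopy | 44.85 | 15 | 3.0 | 8/44.85 = 17.8% | 1.14 |
| Laparoscopy | 44.85 | 20 | 2.2 | 10.5/44.85 = 23.4% | 1.17-1.19 |
| Laparotomy | 104.65 | 10 | 10.5 | 5.5/104.65 = 5.3% | 1.04 |
| All surgery | 149.5 | 15 | 10.0 | 8/149.5 = 5.4% | 1.04 |
| No surgery | 182 | 15 | 12.1 | 8/182 = 4.4% | 1.03 |
| No surgery | 182 | 18 | 10.1 | 9.5/182 = 5.2% | 1.04 |

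In absolute terms, at about ten events per variable the excess is 0.19 points (laparoscopy, k = 4), 0.18 (laparotomy, k = 10) and 0.28 (no surgery, k = 18). At laparoscopy size, mean risk was 4.36% observed against 4.77% predicted with k = 10 (0.41 points), and 4.43% against 5.19% with k = 20 (0.76 points). For scale, the crude 2018 gap between surgery and no surgery is 7.55 − 4.34 = 3.21 points. Restricting to data sets with separation changed little (laparoscopy, k = 10: 9.7% against 9.4% overall).

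**High mortality.** With 200 patients (assumed) and 63% mortality, the 30-day figure Section 4.1 cites for patients without laparotomy in an external cohort, k = 10 gives 62.7% observed and 62.1% predicted. The direction reverses and the shift is small.

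**Who would be affected.** With rare predictors at 2% prevalence (assumed), a rare predictor separated the outcome in about 70% of laparoscopy data sets (k = 10) and 7% of all-surgery data sets (k = 15). With 5% prevalence the figures were 5% for laparoscopy with k = 4 and under 1% for laparotomy with k = 25. The ordering follows from group size; the frequencies depend on the assumptions.

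**After the fix.** With the intercept re-estimated by maximum likelihood and the Firth slopes held fixed, mean predicted equals observed risk in every setting (laparoscopy, k = 10: 4.36% and 4.36%).

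**The case against.** The strongest reply is that the effect is small if the protocol follows its own rule. About 45 laparoscopy deaths allow about four predictors at ten events each, and the excess is then under 5%. A reader might infer inflation of a quarter to a third in small groups. Ratios of 1.24 to 1.33 do arise, but only for an assumed group of 150 patients at 8% mortality with 8 to 12 predictors. That is 12 deaths, or 1.0 to 1.5 events per variable, and neither the group size nor the rate is in the protocol. Those figures mostly describe overfitting. The point stands for the range between. Section 8 applies its rule to the data set and sets no limit per treatment group, while Section 10.1 lists age, demographics, diagnosis, co-morbidities, frailty, vital signs and blood tests, and Section 10.2 adds non-linear terms. More than four predictors in the laparoscopy model is plausible but not certain.

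Other parts of the reply also stand:
- Firth is tied to separation, not to sparse data in general, and may never be used in the larger groups.
- The 4.3% and 7.6% are in-hospital deaths, which Section 8 calls the rarest outcome. The specified model is for 30-day mortality, and more deaths would mean a smaller relative shift.
- Maximum likelihood is not the alternative. Its exact match of mean and observed risk is an in-sample identity, and under separation it has no finite coefficients.

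It can also be said that intercept correction is detail for the statistical analysis plan, which is not shown. That limits the weight of the point. But the protocol itself fixes both the estimator and its predictive purpose, and the planned calibration checks lead to no stated action.

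**Conclusion.** The point holds as a moderate one and should be addressed. Where separation triggers plain Firth, average predicted risk at the 2018 in-hospital rates is overstated: by about 3-5% relative (roughly 0.2-0.3 points) at ten events per variable, and by about 10-20% at laparoscopy size with 10 to 20 predictors. The second figure rests on the assumed predictor count, the assumed covariate effects and a shared 4.3% rate. The ceiling (k + 1)/(2D) needs no assumption about covariate effects.

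Three stronger readings are not supported:
- That Firth always overstates risk. The statement concerns the average, not each patient, and the direction reverses slightly in a group with mortality above 50%, which an end-of-life group might have.
- That the comparison of treatments will be biased against the rarer ones. It may be, if separation occurs in some groups and not in others; the protocol does not give the sizes of all four groups.
- That the group mortality rates are affected. They are direct proportions with 95% confidence intervals (Section 10.2) and do not depend on this choice.

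Naming Firth's correction for separation is itself sound. What is missing is the step from its coefficients to usable predicted risks.

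**What to change.** Add to Section 8 or 10.2 that, where Firth's correction is used, predicted risks come from the Firth fit with its intercept re-estimated by maximum likelihood (FLIC) or from the added-covariate version (FLAC), so that mean predicted risk equals the observed rate. Keep plain Firth for odds ratios. Use the same estimator in all four treatment groups, so that a between-group comparison does not depend on where separation happened to occur.

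The cost is about two sentences of text and one extra fitting step, with no change to the data, the cohort or the crude mortality analysis.
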